Stepped-Wedge Trials are difficult logistically: For all of their associated advantages, stepped-wedge designs are not without challenges including logistical management of multiple sites in varying stages of implementation over time, the possibility of treatment diffusion (to patients initially seen during the control period but receiving follow-up care during the intervention), and the requirement that all sites begin and end evaluation at the same times. Fortunately, Drs. [name] & [name] both have experience with this design in a recent trial assessing implementation and effectiveness of PtDAs for ventricular assistance device therapy.⁴² Also, the baseline survey combined with the importance of getting all sites to start at the same time is why we've included a year of start-up time.

Enrolling 900 patients is overly optimistic: Each site will be expected to enroll 50 patients per year. Because we are implementing a suite of PtDAs, we expect no trouble enrolling the appropriate amount. In our pilot trial at the site with the lowest volume (the Denver VA) we enrolled 9 patients in 6 months for only the initial implant decision aid. We learned that there were many patients getting reimplantation and CRT devices whom were missing. With the suite of PtDAs available in this trial, we think we'll have no trouble enrolling the eligible amount of patients. Also, with our experience with the DECIDE-LVAD trial, we are having more trouble with over-enrollment which is only a problem in rebudgeting to reimburse sites per patient.

What if the study is not successful? If the study does not meet its primary endpoint, our formative evaluation will provide information about potential reasons that it was not successful and lead to better studies of alternative dissemination and implementation strategies for advanced progressive illness. In a pragmatic design such as this, most of the threats (e.g. low reach, low implementation) bias to the null. Indeed, this is precisely why this is a more interesting study than doing a research staff controlled efficacy trial.

How will the PtDAs stay Up-To-Date and Responsive to Perceived Needs? Given the rapid changes in ICD technology, the PtDAs must be kept current to maintain relevance. This will be accomplished via:

- Annual reviews of literature: With incorporation of important changes into the PtDAs.
- Modular design: The sectional build of the PtDAs—clearly defined pages for the pamphlet and segmented video—allows for simple revision as problems are identified or information changes over time.

F. Data Analysis Plan:

Quantitative analysis (Hypotheses 1a, 1b, 1c): The analyses of the effectiveness will use a repeated measures mixed model. This strategy allows for partially incomplete data (e.g. missing follow-up or one of the collection periods) and relaxes the missing data assumptions to missing at

random conditional on observed data. Prior to these analyses, we will contrast the participants in the 2 phases of the study, identifying any patient/site characteristics that are unbalanced. If more than 3-5 variables are identified, we will develop a propensity score for the likelihood of being in the intervention phase. Each analysis model will include an indicator variable for the intervention phase, indicators for each of the sites and the variables identified above.

Sample Size and Power Calculation: This trial was designed to have diversity in implementation settings. As such, to effectively be powered to explore implementation across diverse settings, we are overpowered to test our primary quantitative outcomes (the knowledge domain of decision quality). With a sample size of 900 patients and a standard deviation of 18%, achieved power would approach 1.00 to detect a 10% improvement in knowledge (in the 2011 Cochrane Review, knowledge improved an average of 13.8%, in our pilot trial, knowledge improved 12%).⁶ Even with variance inflation for correlation within sites (assuming intraclass correlation 0.01), the power remains good at 0.98. This level of power will afford the ability to assess some heterogeneity of effect across sites and vulnerable patient groups, as well as adequate assessment of secondary effectiveness measures and implementation evaluation. To test the hypothesis that better informed patients will have less anxiety (hypothesis 1c), we will correlate the knowledge score with the HADS- A. Using a Pearson's correlation coefficient, for a sample size of 300 (based on 1/3 illustrating significant anxiety) then the person's correlation is 0.18 for a power of 90% and an alpha of 0.05.

G. Summarize Knowledge to be Gained:

We have designed the implementation to use and leverage existing resources to implement the intervention. Further, we have designed the study as an effectiveness/implementation study with emphasis on formative evaluation. Together, it is our hope that if the intervention is successful, we will develop an implementation guide and online distribution of materials for other ICD programs and other practitioners interested in testing and disseminating effective therapies.

The lessons learned herein will apply broadly. As discussed in the Significance section, policies are changing. Patients are increasingly demanding involvement and seeking additional sources of information. The PtDA development group in Colorado has been contracted by the American College of Cardiology to develop a PtDA for patients with severe aortic stenosis considering surgical versus transcatheter repair. The American College of Cardiology has also inquired with Colorado about developing a tool for the recently approved left atrial appendage occlusion device. Science on real-world effectiveness and implementation is essential in informing the field of PtDA delivery for high risk medical conditions.

H. Bibliography & References Cited:

1. Alston, C. Shared decision-making strategies for best care: Patient decision aids: The Institute of Medicine; 2014.
2. The Institute of Medicine. Crossing the Quality Chasm: A New Health System for the 21st Century. Washington D.C.: National Academy Press; 2001.
3. The Patient Protection and Affordable Care Act. 2010.
4. Patient Preference Information. The Food and Drug Administration, 2015. (Accessed 05/24/2016, at <http://www.fda.gov/downloads/MedicalDevices/DeviceRegulationandGuidance/GuidanceDocuments/UCM446680.pdf>.)
5. Decision Memo for Screening for Lung Cancer with Low Dose Computed Tomography (LDCT) Centers for Medicare and Medicaid Services; 2015.

6. Proposed Decision Memo for Percutaneous Left Atrial Appendage (LAA) Closure Therapy. Centers for Medicare and Medicaid Services; 2015.
7. Tuckett D. et al. Meeting Between Experts: An Approach to Sharing Ideas in Medical Consultations. London: Tavistock Publications; 1985.
8. Rosenbaum L. The Paternalism Preference--Choosing Unshared Decision Making. *N Engl J Med* 2015;373:589-92.

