For values items, we found that patients would rate competing values (such as dying quickly or living as long as possible) very highly when asked as single items, leaving little variability in responses. When forced to choose on a visual analogue scale, however, we found that groups of patients would discriminate their preferences. In total, the values items included herein account for 53% of the variance in relevant patient values. This item will be used to assess value-concordance going forward.

[name]'s dissertation: In his doctoral dissertation,⁵⁸ [name] surveyed current defibrillator patients at the University of Colorado (with the guidance of [name] - PI) to conceptualize relationships between how patients learned about their ICDs, how well they understand benefits and risks associated with ICD therapy, and QOL. In addition to creating new ICD knowledge and informational media history measures, the data gathered in this project highlighted group-based differences in treatment knowledge and information-seeking behavior. When compared to their younger counterparts, the oldest patients in the sample (age >71.5) both used fewer forms of media to learn about their ICD (being particularly less likely to use online information) and scored lower on a treatment knowledge measure, as did participants who did not complete high school when compared to those with at least a college degree. Significant depression and anxiety were also highly prevalent in this sample of patients (58% and 39.5%, respectively), and depression illustrated high statistical collinearity in models predicting patients' QOL. [name] continues to analyze whether this association indicates that depression drives QOL among ICD patients to a greater extent than previously thought, and/or the possibility that depression mediates other factors' influence on QOL.

Hartford-sponsored symposium on older adults: In 2014, Drs. [name] and [name] received funding from the Hartford Foundation to host a multi-disciplinary symposium of researchers to discuss the practice and research agenda for older adults considering ICDs. The proceedings from this symposium highlighted many aspects of ICD research and practice, including the importance of SDM for ICDs.⁴⁹

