- 3) Balanced and standardized patient and caregiver testimonials: We made an explicit decision to include patient narratives in our PtDAs. First, in our needs assessment, many patients stated that they wanted to hear from other patients. Second, biased narratives from industry and other sources are abundant on the internet - by including tested and controlled narratives, we were able to ensure honesty in the messages patients receive.⁶⁸ We were aware of concerns that narratives may be overly biasing.⁶⁹ To avoid this, we chose to include only process narratives (e.g., “Here is how I made my decision”) and avoid outcome narratives (e.g., “This is the best/worst decision I’ve ever made”).⁷⁰
- 4) Combined pamphlet and video PtDAs: The combined format of a pamphlet and video was chosen based on our prior work and designed to fit diverse clinical contexts. Further, some data suggests that videos are better for patients with lower health literacy.⁷¹
- 5) Design for implementation: While we followed IPDAS guidelines, our iterative development process utilized a user-centered design perspective with both patients and clinicians. Consistent with user-centered design principles, feedback from users took precedence over IPDAS guidelines specifically for the purpose of facilitating future implementation.^{72,73}

Pilot trial of the ICD PtDAs: 21 patients enrolled; 15 were randomized to the intervention. 67% found the PtDAs to be unbiased, 22% found them biased toward ICDs, and 11% found them biased toward not getting an ICD. Furthermore, 89% found the PtDAs helpful, and 100% would recommend them to others. The pilot was feasible at all sites; however, using clinic staff to identify eligible patients was more efficient than research assistants conducting chart review. Intervention patients had trends towards improvements in both domains of decision quality: greater knowledge about ICDs ($M=14.0/20$ vs. $11.6/20$, *ns*) and increased concordance between their decision and values (71% concordant vs. 29%, $p=0.06$).³⁴

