Reach: Reach is defined as the proportion of the target population who participate in the intervention. While this is a straightforward measure, defining the denominator of eligible patients is surprisingly difficult. We will assess the percentage of patients that both receive and remember reviewing the PtDAs. Representativeness will be assessed by comparing participants to those who opt out on a range of available demographics and clinical indicators (e.g., age, gender, comorbidities) from chart review. As we are only enrolling a subset of patients into the trial at each site, we will ask the staff delivering the PtDAs to maintain a log of intervention recipients. We will obtain a waiver of consent to calculate aggregate reach at each site among all patients receiving ICDs.

Effectiveness:

- Primary outcome: Decision quality is an essential element of the Ottawa Decision Support Framework (Figure 2), defined as “the extent to which the implemented decision reflects the considered preferences of a well-informed patient.”⁵⁵ Decision quality measures consist of two domains: knowledge and values.
 - Knowledge: Consistent with methods developed by Sepucha et al.,^{55,56} we have developed a knowledge measure. We will use this measure to test knowledge at baseline and at 1 months and 6 months.
 - Value-treatment concordance: We will calculate concordance between patients’ values and the treatment they choose according to the validated methods of Sepucha et al.^{55,56} We will measure this in two ways: 1) we will measure the values-clarity subscale of the decision conflict measure (test-retest reliability and Cronbach’s alpha > 0.78, correlated with knowledge, regret, and treatment discontinuance) and 2) we will explore the prevailing value trade-off between “living longer even if it means getting an invasive therapy” versus “not living as long and avoiding an invasive therapy” as this item was able to discriminate between groups.
- Secondary outcomes: Additionally, we will collect the following secondary outcomes:
 - IPDAS process measures: We will use seven questions based on key domains of decision process as outlined in the IPDAS background document. [name] used these questions in his prior survey and they had significant reliability (Cronbach’s alpha of 0.78).⁷⁴
 - Decision choice: We will use single item measures of decision predisposition, choice, and enactment. These questions have test-retest reliability of 0.9 and correlates with values.^{75,76}

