 - Self-efficacy: The ‘Decision Self-Efficacy Scale’ measures self-confidence or belief in one’s ability to make decisions, including participate in shared decision making.⁷⁷
 - Control Preferences: This is a 2 question measure of a patient’s opinion of their preferred and actual role in decision-making.⁷⁸
 - The Decision Conflict Scale (DCS): DCS is a 10-item instrument that measures decision quality and determines decisional uncertainty.⁷⁹ The DCS quantifies personal perception of: a) uncertainty in choosing options; b) modifiable factors contributing to uncertainty such as feeling uninformed, unclear about personal values, and unsupported in decision making, and c) effective decision making such as feeling the choice is informed and values-based, and expressing satisfaction with the choice. DCS reliability measures include test-retest correlation and Cronbach’s alpha coefficients exceeding 0.78-0.90^{30,74}. The DCS discriminates between groups who make and delay decisions.³⁰

- The Decision Regret Scale: Decision regret is a 5-item scale which measures regret with the decision making. It is a commonly used measure in decision aid trials and has good reliability (Cronbach's alpha of 0.82-0.91).^{30,74} It correlates with satisfaction, decision conflict, and QOL.⁸⁰
- The Patient Health Questionnaire-2 (PHQ-2): This comprises the first 2 items of the PHQ-9, inquires about the degree to which an individual has experienced depressed mood and anhedonia over the past two weeks.⁸¹
- The Generalized Anxiety Disorder Scale (GAD-2): In primary care patients, the Generalized Anxiety Disorder scale (GAD-7) had high sensitivity for detecting generalized anxiety disorder and panic disorder. The GAD-2 had high sensitivity and specificity for GAD and high specificity for panic disorder, social anxiety disorder, and post-traumatic stress disorder.⁸²
- ICD experiences: These will be questions developed and used previously to describe ICD-specific issues such as whether the participant has experienced a shock or complication and whether they have considered discussing their ICD in an advance directive or with a surrogate decision maker.

B. Description of Population to be Enrolled:

Inclusion Criteria:

1. The participants in the trial will be adult (age ≥18) patients who have been offered a primary prevention ICD for initial implant, reimplantation, or CRT with defibrillation. Primary prevention must be for heart failure.

Exclusion Criteria:

1. Under 18 years of age

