Stepped-wedge multicenter trial (Table 3): We considered three potential designs for this trial. A classic patient-level randomization is not possible since programs (rather than patients) are effectively the primary targets of intervention implementation. The traditional cluster randomized trial would be disadvantaged by the small number of sites. Therefore, we propose a multicenter trial that is randomized at the clinic-level for a phased rollout of the shared decision support intervention.^{42,84} A variant of the cluster trial design, the stepped-wedge trial design is a one-way crossover cluster trial where all the groups will receive the intervention, but the time of intervention is randomly ordered. It is a compelling choice of design when 1) one of the goals is to study intervention implementation, 2) the intervention is thought to be efficacious, 3) all sites wish to receive the intervention and continue its implementation after the trial if it is effective, and 4) contamination/diffusion of the intervention effects to other subjects is likely. The stepped-wedge design is more efficient in terms of statistical power when compared to the classical cluster randomized design because the impact of the intervention is estimated using both within and between cluster differences.

Table 5: Measures	Baseline Pre Decision	1 Month Post Decision	6 Months Post Decision
-------------------	-----------------------	-----------------------	------------------------

COVARIATES			
- Demographics (combined survey and short chart review)	X		
- Medications, Comorbidities, Heart Failure Type/Severity	X		X
- Literacy (REALM-R 7 item) ⁸⁵ and Subjective Numeracy ⁸⁴	X		
EFFECTIVENESS OUTCOMES (see descriptions below)			
- Decision Quality – Knowledge	X	X	X
- Decision Quality – Value-concordance	X	X	X
- Decision Process		X	X
- Decision choice		X	X
- Self-Efficacy Scale	X	X	X
- Control Preferences	X	X	X
- Decision conflict	X	X	X
- Decision regret		X	X
- PHQ-2	X		X
- GAD-2	X		X
- ICD Experiences (+/- shock; +/- complications etc.)		X	X

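### One of the two measures listed for value-treatment concordance rates clarity about values, not agreement with the treatment chosen; the other has no scoring rule, and the baseline entry is undefined.

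*Combined protocol and SAP*

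**What the plan says.** Section IV.A, under the primary outcome, states: "Decision quality measures consist of two domains: knowledge and values". For the values domain it commits to a comparison with treatment: "We will calculate concordance between patients’ values and the treatment they choose". It cites published methods for this and then gives two ways of measuring it. The first: "we will measure the values-clarity subscale of the decision conflict measure". The second is a trade-off item that sets longer life with an invasive therapy against shorter life without one. The plan says only that this item will be explored.

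Three other places bear on the point.

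- Section III, on the development of the decision quality measure, reports values items answered as a forced choice on a visual analogue scale and concludes: "This item will be used to assess value-concordance going forward".
- The secondary outcomes in section IV.A include the full Decision Conflict Scale (DCS) ("DCS is a 10-item instrument that measures decision quality and determines decisional uncertainty") and "single item measures of decision predisposition, choice, and enactment".
- Table 5 in section IV.C has a row "Decision Quality – Value-concordance" marked at baseline, 1 month and 6 months. Its decision choice row is marked at 1 and 6 months only.

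**The concern.** Section III defines a quality decision by whether the treatment chosen fits the values of an informed patient. A score that does not use the treatment cannot report on that fit. If values clarity is presented as concordance, a rise in felt clarity could be read as evidence that decisions match values better, when the data would not show it.

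The protocol's own survey of patients with ICDs illustrates the gap. Of those surveyed, 61% preferred a quick death and a shorter life to a long life ending in slow decline, which the protocol regards as opposed to what the device does. Such patients may be quite clear about their values and still hold a device that conflicts with them. The survey result as reported says nothing about clarity, so this is an illustration and not an estimate.

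The measure that could show concordance has no scoring rule and no stated rank, so its definition could be settled after the data are seen.

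**Working it through.** The plan gives no sample size, power or expected effect for concordance, so there is no figure to reproduce. The check compares the stated construct with the stated measures.

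**1. What the construct needs.** By sections III and IV.A it needs two inputs per patient: the option favoured by the patient's values (V) and the treatment (T). Concordance is C = 1 if T is the option that V favours, and 0 otherwise.

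**2. What the first measure uses.** Section IV.A describes the DCS as quantifying personal perception, including being unclear about one's values. The values-clarity subscale is thus a rating S of felt clarity, and no passage brings T into it. Take two patients with the same V and the same S, one with an ICD and one without. S is identical, but C is 1 for one and 0 for the other. S alone therefore cannot determine C.

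**3. What the second measure uses.** The trade-off item supplies V. Choice and enactment, listed among the secondary outcomes, supply T. Both inputs are in the plan. What is missing:
- a rule that combines them;
- a cut-off, if the item is answered on a visual analogue scale as in section III;
- whether T is the choice stated or the choice enacted;
- which of the two listed measures ranks first.

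**4. When C can be computed (Table 5).**

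| Row | Baseline | 1 month | 6 months |
|---|---|---|---|
| Value-concordance | X | X | X |
| Decision conflict | X | X | X |
| Decision choice | – | X | X |
| C computable | no | yes, given a rule | yes, given a rule |

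**5. Status of the domain.** Section IV.F names knowledge as the primary quantitative outcome and powers only that: 900 patients, SD 18, difference 10, intraclass correlation 0.01, power 0.98. With 450 per phase and two-sided alpha 0.05 (both assumed) and 6 sites of 150, the design effect is 1 + 149 × 0.01 = 2.49. The test statistic is then 10 / (18 × √(2 × 2.49/450)) = 5.28. Power is 0.9996 by the normal approximation and 0.970 with a t reference on 4 df, so the stated 0.98 is broadly reproduced for knowledge.

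It does not carry over to a binary outcome. Under the same assumptions, for a 10-point rise in the proportion concordant:

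| Assumed proportions | Power, no clustering | Power, design effect 2.49 |
|---|---|---|
| 50% to 60% | 0.856 | 0.480 |
| 60% to 70% | 0.883 | 0.513 |

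The proportions are assumptions, and the design effect is the simple cluster formula, not a stepped-wedge variance. The figures show only that power for concordance needs its own calculation.

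**The case against.** The strongest reply is that the plan commits to calculating concordance with the treatment chosen, cites published methods, and lists a trade-off item as well as the subscale. Choice and enactment are collected at both follow-ups, and the scoring rule may be in the cited papers, which were not available here. This stands to a large extent. A reader might infer that the whole domain cannot show concordance; the documents do not support that, because the ingredients are there at 1 and 6 months.

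A reader might also infer that the undefined baseline value blocks the repeated-measures analysis. It does not. The model in section IV.F tests an intervention-phase indicator, tolerates incomplete data and does not require a baseline concordance value. The values item and the subscale can both be answered at baseline, so the Table 5 entry may have been meant that way.

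Third, the pilot reported "increased concordance between their decision and values" (71% against 29%), and the 42-point gap might be taken as the size of what is at stake. It is not. The pilot had 21 patients and p = 0.06, and the protocol does not say how concordance was scored. With 15 of 21 in the intervention group, 6 remain, and no count out of 6 or fewer rounds to 29%, so the denominators are unknown.

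Other limits also stand. The subscale's items are not printed, so its content is inferred from its name and the description of the DCS. The item in section III is illustrated by quick death against long life, and the one in section IV.A concerns invasive therapy; they may not be the same item. Reporting a subscale beside its parent scale is not in itself an error.

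None of this answers the central point: the first-listed measure does not fit the construct it is listed under, and no rule is given for the other.

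**Conclusion.** The point holds in limited form. One of the two listed measures is a clarity rating that cannot by itself show concordance as sections III and IV.A define it. The other could, once crossed with choice or enactment, but has no rule and is only to be explored. Concordance is undefined at one of its three scheduled time points, the pre-decision baseline; the 1- and 6-month comparison remains feasible.

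No numerical effect on the trial's result can be derived from the documents. The conclusion rests on reading the subscale as its name and the description of the DCS indicate, and on no scoring rule being given in the protocol itself.

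A reader might go further and infer that hypothesis 1b could be declared met on clarity alone. No passage says so. Since section IV.F names and powers knowledge only, the supportable statement is that the standing of concordance within the primary outcome is unclear.

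**What to change.** 1. In section IV.A, define value-treatment concordance as agreement between the trade-off answer and the treatment at 1 and 6 months. State whether treatment means the choice made or the choice enacted, and prespecify a cut-off if the answer is on a visual analogue scale. Name the same item in sections III and IV.A.
2. In section IV.F, compare concordance between phases with a mixed model for a binary outcome, using the phase and site terms already listed there.
3. Report values clarity as a secondary outcome within the DCS, and not as concordance.
4. State whether concordance is co-primary with knowledge. If it is, give it its own power calculation.
5. In Table 5, relabel the baseline value-concordance entry as values items only.

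The cost is protocol and analysis-plan wording; the items needed are already collected. The downside is that a binary outcome is less precise than a scale score, so power for this domain may be well below that stated for knowledge.

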- Patients declining ICDs expressed concerns that the numbers didn't apply to them and/or the benefits were not enough: "It's like walking around with a motorcycle helmet on when you're driving your car." One patient addressed the trade-off between dying sooner from sudden death and living longer and dying of progressive heart failure: "Going into my decision is also the fact that I can't work because of my medical condition. I can't work at the hospital; I can't work at the church. My life is sitting here and watching TV... to take a defibrillator would just lengthen the process that I don't really want lengthened."
- Behavioral economics were applied via a framework analysis of two sets of interviews. We found evidence of cognitive bias in decision making, including patients attributing a halo effect to a clinician, who then presents a status quo bias to perform an ICD in the context of influential framing techniques. Taken together, the biases appeared to encourage ICD treatment.(under review)

Development of a measure of decision quality: Decision quality is an essential element of the Ottawa Decision Support Framework (Figure 2) defined as "the extent to which the implemented decision reflects the considered preferences of a well-informed patient."⁵⁵ Accordingly, a decision is "a quality decision" if the treatment chosen is concordant with a knowledgeable patient's values.^{55,56} Some have proposed that measures of decision quality be included in the pay for performance agenda⁵⁷ and the Affordable Care Act calls for "the development of quality measures that allow for the assessment of the experience, quality, and use of information provided to and used by patients..."³ We developed a measure of ICD decision quality using a robust process of patient and clinician assessment to determine the key knowledge items (content validity). We then tested this measure on a large population of patients and determined test-retest reliability ($r=0.56$, $p>.01$) and internally-reliable assessment of patient knowledge ($\alpha=.61$). We demonstrated discriminant known-groups validity of the knowledge measure by showing that clinicians scored better than patients with ICDs who scored better than patients without ICDs (98% vs. 60% vs. 40% mean scores, respectively).

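### Patient-level covariates enter the effectiveness models only through an undefined balance screen, so likely predictors of knowledge have no assured place

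*Combined protocol and SAP*

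**What the plan says.** Section IV.F (Data Analysis Plan, quantitative analysis) states: "The analyses of the effectiveness will use a repeated measures mixed model". Covariates are then chosen in three steps.

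- Screening: "we will contrast the participants in the 2 phases of the study, identifying any patient/site characteristics that are unbalanced".
- A branch: "If more than 3-5 variables are identified, we will develop a propensity score for the likelihood of being in the intervention phase".
- The model: "Each analysis model will include an indicator variable for the intervention phase, indicators for each of the sites and the variables identified above".

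No test, cut-off or list of candidate variables is given, and no patient-level covariate is fixed in advance. Table 5 in section IV.C has a covariate block (demographics, medications, comorbidities, heart failure type and severity, literacy, numeracy). It is a collection schedule that is not tied to the model, and it does not name decision type or prior ICD.

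Section IV.B enrols "patients who have been offered a primary prevention ICD for initial implant, reimplantation, or CRT with defibrillation". Section IV.A and Table 5 have knowledge measured at baseline, 1 month and 6 months. Section IV.F does not say whether the baseline score is a covariate, a response or unused.

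**The concern.** A covariate improves precision when it predicts the outcome, whether or not it happens to be balanced. A screen on balance alone drops predictors when the phases look alike, and it can miss a modest real shift.

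The documents point to several likely predictors. In the development of the knowledge measure (section III), clinicians scored best, followed by "patients with ICDs who scored better than patients without ICDs (98% vs. 60% vs. 40% mean scores, respectively"). That is a 20-point gap by prior ICD, and this trial mixes first implants with reimplants. The dissertation survey in section III links older age and less education to lower scores on a separate knowledge measure. Baseline knowledge is an obvious further candidate.

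The criterion is undefined and the propensity trigger is a range, so two competent analysts could fit different primary models to the same data. The same rule governs every effectiveness model. That includes the secondary and subgroup questions on which section IV.F intends to spend the trial's surplus power.

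**Working it through.** **1. The plan's own power figure.** Inputs from section IV.F: N = 900, SD 18, difference 10, ICC 0.01. Equal phases of 450 and two-sided alpha 0.05 are assumed.

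- Without clustering: SE = 18 × √(2/450) = 1.20 and 10/1.20 = 8.3, so power exceeds 0.9999 (plan: approaching 1.00).
- With 6 sites of 150: design effect = 1 + 149 × 0.01 = 2.49; effective n per phase = 450/2.49 = 181; SE = 1.89; ratio 5.28. Power is 0.9996 (normal), 0.985 (t, 5 df) or 0.970 (t, 4 df), against the plan's 0.98.

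The figure reproduces to within 2 points. Power is not the issue.

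**2. How often would decision type be left out?** The reimplant share is assumed equal to the national one in section II: 70,000/(130,000 + 70,000) = 35%. The SE of the difference in share between phases is √(0.35 × 0.65 × 2/450) = 0.0318.

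- If the screen were p < 0.05, the largest unflagged difference would be 1.96 × 0.0318 = 6.2 percentage points. Decision type is left out 95% of the time with no true shift. With a true 5-point shift it is left out 65% of the time, since 0.05/0.0318 = 1.57 and Φ(1.96 − 1.57) = 0.65.
- If the screen were a standardised difference above 0.1, it is left out about 87% of the time with no true shift.
- Simulation with site-to-site SD in share of 5 to 15 points and/or a 10-point drift over the trial: left out 55–91% (p < 0.05) or 43–80% (0.1 rule).

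**3. What adjustment would gain, and what a missed shift is worth, without baseline knowledge in the model.** Share of variance = 0.35 × 0.65 × gap²/18². SE cut = 1 − √(1 − share). Missed shift = 0.0623 × gap.

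| Follow-up gap | Share of variance | SE cut | Missed shift |
|---|---|---|---|
| 2 points | 0.003 | 0.1% | 0.12 points |
| 10 points | 0.070 | 3.6% | 0.62 points |
| 20 points | 0.281 | 15.2% | 1.25 points |

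The 20-point row is an upper bound. The 60% and 40% were not measured 1 and 6 months after an ICD decision. In the pilot ("21 patients enrolled; 15 were randomized to the intervention"), knowledge was reported as "greater knowledge about ICDs ($M=14.0/20$ vs. $11.6/20$, *ns"). The comparison group, 21 − 15 = 6 patients, therefore scored 11.6/20 = 58%, with timing not given. Against 60% for patients with ICDs, that would be a gap of only 2 points.

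**4. With baseline knowledge adjusted.** The correlation is assumed to be 0.56, borrowed from the test-retest figure in section III. Missed shift = (follow-up gap − 0.56 × baseline gap) × 0.0623.

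| Baseline gap to follow-up gap | Further SE cut | Missed shift |
|---|---|---|
| 20 to 20 | 5.7% | +0.55 points |
| 20 to 10 | 0.1% | −0.07 points |
| 20 to 2 | 6.2% | −0.57 points |
| 2 to 2 | 0.04% | +0.05 points |

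The gain is not monotone, so baseline adjustment alone does not settle the matter.

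**5. Should named covariates replace the imbalance set or join it?** Simulation: 6 sites, 8 periods, 864 patients, one follow-up score, site indicators, p < 0.05 screen, true effect 10, decision-type gap 10. A further predictor that is not on the named list is worth 10 points and shifts by 10 percentage points between phases.

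| Primary model | Mean estimate | RMSE |
|---|---|---|
| Plan's rule | 10.07 | 1.34 |
| Decision type only, no imbalance set | 11.03 | 1.67 |
| Decision type plus imbalance set | 10.07 | 1.30 |

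Replacing the set is worse than the plan. Adding to it was no worse than the plan in any scenario run.

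**The case against.** The sponsor has good answers to the stronger readings.

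- A reader might infer that decision type will usually be left out. The documents do not support that: no criterion is stated, and the low end of the range tried is under half. The screen also covers any patient or site characteristic, and decision type is known from eligibility, so nothing suggests it would be overlooked.
- A reader might infer that the primary model is picked with an eye on the result. Section IV.F places the comparison of phases before the effectiveness analyses and names only patient and site characteristics. This is a gap in prespecification, not outcome-driven selection, and it does not in itself inflate type I error.
- The size is not established. The gap in knowledge after a decision is not in the documents, and the results run from nothing to modest.
- The imbalance step has a purpose. Sites, not patients, are randomised, there are only six, and section IV.B concedes that enrolment is not completely random. Imbalance between phases may be confounding, and the step guards against it. Moving it to a sensitivity analysis would remove that guard, as step 5 of the working shows.

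All four stand. They limit the point and shape the remedy. They do not answer the text itself: there is no criterion, the trigger is a range, and no predictor is assured a place.

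**Conclusion.** The point holds as a worthwhile improvement to the analysis plan, not as a threat to the trial's main conclusion. Selecting covariates on balance alone can leave out likely predictors of knowledge, and the rule is too loosely stated to give one primary model.

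The cost has three parts:

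- Precision: an avoidable loss equal to an SE cut of about 0% to 15%, depending on the gap after the decision and on how baseline knowledge enters.
- Bias: about 1 point at most (1.25 in the extreme case) against the 10-point target, possibly near zero and of either sign.
- Discretion: the analyst settles the criterion and the propensity trigger.

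These sizes rest on 450 patients per phase, a 35% reimplant share, SD 18, an assumed screening rule and, with baseline adjusted, a correlation of 0.56. The simulation in step 5 also takes complete data and no separate period effects. The finding that the rule is undefined and fixes no patient-level covariate rests on the text alone.

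**What to change.** In section IV.F:

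1. Include in every effectiveness model, whatever the observed balance, decision type (initial, reimplant, CRT-D) or prior ICD, age and education. Add baseline knowledge where it is measured before the decision aid is given. The documents place the baseline survey before the ICD decision but do not say that it precedes the aid, so this should be stated.
2. State how baseline knowledge enters the repeated-measures model. If it is a response, let the decision-type effect differ between baseline and follow-up.
3. Keep the imbalance-selected covariates or the propensity score in the primary model in addition to these, not as a sensitivity analysis.
4. Fix one imbalance criterion and one trigger for the propensity score before the phases are compared.

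The cost is SAP wording and a few degrees of freedom out of about 900 patients. Age, education and baseline knowledge are already collected, and decision type is known at eligibility.
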